## **9. STUDY EVALUATIONS**

### **9.1. Study Procedures**

Refer to Section [9.1.6](#) for the procedures to be followed in case of a study pause and to Section [9.1.7](#) for procedures to be followed for subjects participating in the Cohort 1 substudy.

#### **9.1.1. Overview**

The [Time and Events Schedule](#) summarizes the frequency and timing of safety, tolerability and immunogenicity measurements and evaluations applicable to this study. Details for all study procedures are provided in the following sections. Additional unscheduled study visits may be required if in the investigator's opinion, further clinical or laboratory evaluation is needed.

#### **Visit Windows**

The screening visit has to be performed within 8 weeks prior to the baseline visit (ie, the day of the subject's prime vaccination, Day 1). If a subject did not receive study vaccine on the planned day of vaccination, the timings of the next visits post-vaccination (see [Time and Events Schedule](#)) will be determined relative to the actual day of vaccination. Visit windows that will be allowed are summarized in [Table 3](#). The subject should be encouraged to come within these time windows.

**Table 3: Visit Windows**

Visit Description	Day	Window
Seven Days Post-prime Vaccination	Day 8 for all groups	±2 days
Fourteen Days Post-prime Vaccination (only in Groups 2 and 3 from Cohort 1)	Day 15 for Group 2 and Group 3	±2 days
Boost Vaccination	Day 29 for Group 1 Day 57 for Group 2 Day 85 for Group 3	±3 days
Seven Days Post-boost Vaccination	Day 36 for Group 1 Day 64 for Group 2 Day 92 for Group 3	±2 days
Twenty-one Days Post-boost Vaccination	Day 50 for Group 1 Day 78 for Group 2 Day 106 for Group 3	±3 days
Forty-two Days Post-boost Vaccination	Day 71 for Group 1 Day 99 for Group 2 Day 127 for Group 3	±3 days
Follow-up 6 Months Post-boost a	Day 209 for Group 1 Day 237 for Group 2 Day 265 for Group 3	±15 days
Follow-up 1 Year Post-prime	Day 365 for all groups	±30 days

Refer to [Table 6](#) (Section 9.1.7) for the visit windows that will be allowed for the Cohort 1 substudy.

a Subjects who completed the 6-month post-prime visit (which has been replaced with the 6-month post-boost visit per protocol Amendment 2) prior to approval of Amendment 2 were required to also attend the 6-month post-boost visit after approval of Amendment 2.

## Blood Sampling Volumes

Approximately 200 to 400 mL of blood (including PBMC samples) will be drawn from adults and adolescents (12-17 years of age inclusive) over a period of 1 year, and remains well below the limits of standard blood donation.

For children (<12 years), the study-related blood volumes obtained (including any losses during phlebotomy) will not exceed 3% of the total blood volume during a period of 4 weeks. In order to meet the planned safety, serologic and cellular endpoints, it might be necessary to slightly exceed the guideline of 1% of the total blood volume at any single time. The sites will be instructed that the procedures should preferably be performed in the following order, according to their importance: safety, serology and cellular. The total volume of blood is estimated at 80 to 90 mL/kg body weight; 3% is 2.4 mL blood per kg body weight. The allowable blood volume calculations are based on the 10th percentile for growth charts for 4- to 11-year-old children.

For details on the approximate blood sampling volumes collected by visit and the cumulative blood volumes in Cohorts 1 and 2, refer to the [Time and Events Schedule](#). For Cohort 3, the approximate blood sampling volumes collected by visit and the cumulative blood volumes for the immunogenicity assessments are provided in the [Time and Events Schedule](#), while the site's Standard Operating Procedure will be followed with regard to the blood volumes for the clinical laboratory assessments.

Additional serum or urine pregnancy tests may be performed, as determined necessary by the investigator or required by local regulation, to establish the absence of pregnancy at any time during the subject's participation in the study.

Repeat or unscheduled samples may be taken for safety reasons or for technical issues with the samples.

### **9.1.2. Screening Phase**

Up to 8 weeks before baseline (the day of the subject's prime vaccination, Day 1) and after signing and dating the ICF and/or assent (see Section 16.2.3), screening assessments will be performed as indicated in the [Time and Events Schedule](#). Screening may be split into multiple days or visits. In exceptional cases, the screening phase can be extended if discussed with and approved (documented) by the sponsor, eg, if not all the test results become available during the allocated 8 weeks; this will be evaluated on a case-by-case basis.

For male subjects and female subjects of non-childbearing potential, there will be no minimum duration of the screening period and it will last only for the time required to verify eligibility criteria. For female subjects of childbearing potential, it should be confirmed that adequate birth control measures were used from at least 28 days before the prime vaccination with a negative serum  $\beta$ -hCG pregnancy test at screening and a negative urine test immediately prior to each study vaccination (see Section 4). All male and female subjects, except for female subjects of non-childbearing potential, will be asked to use adequate birth control for sexual intercourse until at least 3 months after the prime vaccination or up to 1 month after the boost vaccination (whichever takes longer) (see Section 4.3).

Only subjects complying with the criteria specified in Section 4 will be included in the study. The investigator will provide detailed information on the study to the subject and will obtain written informed consent/assent prior to each subject's study participation. The procedures indicated in the [Time and Events Schedule](#) will only be performed after the subject's written informed consent/assent has been obtained.

After reading but before signing the ICF/assent, the TOU will be administered. Subjects who fail may repeat the test twice (and have to pass the third time to be eligible). Subjects must pass the TOU before starting the screening procedures. The TOU is a questionnaire to document the subject's understanding of the study (for details, see Section 16.1).

The following is performed to determine eligibility requirements as specified in the inclusion and exclusion criteria:

- Review of all inclusion and exclusion criteria;
- Review of medical history (including concomitant diseases) and demographics;
- Review of prestudy therapies (up to 30 days prior to the start of screening), previous vaccinia/smallpox vaccination if known (at any time prior to study entry; not applicable for Cohort 3) and concomitant therapies;

- Serum pregnancy test (for female subjects of childbearing potential);
- Blood sampling for hematology and chemistry (fasting or non-fasting);
- Urine sampling for urinalysis;
- Serology testing: HIV type 1 or type 2 (for Cohorts 1, 2b, and 3 only);
- CD4+ cell count for HIV-infected subjects;
- FSH assessment (for women  $>45$  years of age with amenorrhea for less than 2 years or  $\leq 45$  years of age with amenorrhea for more than 6 months);
- ECG recording for subjects  $\geq 18$  years of age;
- Full physical examination (including height and body weight; a genitourinary examination is not required);
- Measurement of vital signs (blood pressure, pulse/heart rate, body temperature).

All adverse events and pregnancies will be collected from the time a signed and dated ICF is obtained.

The overall eligibility of the subject to participate in the study will be assessed once all screening values and results of any other required evaluations are available. Retesting of values (eg, safety laboratory) that lead to exclusion is allowed once using an unscheduled visit during screening to assess eligibility. The safety laboratory assessments are to be performed within 28 days prior to the prime vaccination (including Day 1 before vaccination) and may be repeated once if they fall outside this time window. If rescreening is required, all screening procedures (except TOU) should be repeated. Study subjects who qualify for inclusion will be contacted and scheduled for enrollment and prime vaccination within 8 weeks.

### **9.1.3. Vaccination Phase (Prime and Boost)**

If eligible, the subject will come for the baseline visit (Day 1). The investigator should ensure that all enrollment criteria have been met during screening. If a subject's clinical status changes (including available laboratory results or receipt of additional medical records) after screening but before the prime vaccination (Day 1) such that the subject no longer meets all enrollment criteria, then the subject should be excluded from further participation in the study. If the initial laboratory sampling occurred more than 8 weeks before baseline (Day 1), sampling will need to be repeated.

Eligible subjects will be allocated (by central randomization) to a vaccination schedule as described in Section 5.

The subjects will be vaccinated as described in Section 6, with prime vaccinations administered at Day 1 for all groups, and boost vaccinations at Day 29 (Group 1), Day 57 (Group 2) or Day 85 (Group 3) unless any of the pre-specified criteria not to proceed with vaccination are met (refer to Sections 6.2, 6.3 and 10.2 for details) or if a pause for vaccination of further subjects has been installed (see Section 9.3.2).

Before each vaccination (prime and boost), a urine pregnancy test (for female subjects of childbearing potential), a targeted physical examination and measurements of vital signs will be performed and blood will be drawn for safety and immunogenicity assessments. Refer to Section 9.4 for further details on the immunogenicity evaluations.

Study vaccine will be prepared on-site by unblinded qualified study-site personnel not involved in any other study-related procedure who will place a blinding tape on the syringe to mask its content and send the vaccine to a blinded study vaccine administrator (see [Definitions of Terms](#)) for administration to the subject (see Section 14.3 for details). Refer to Section 6 for further details on dosage and administration and post-vaccination monitoring.

All adverse events, serious adverse events, IREs and pregnancies will be collected and documented on the CRF, together with the information on any concomitant medications. For reporting of IREs, refer to Section 12.3.3.

Upon discharge from the site, subjects will be provided with a diary, a thermometer, and a ruler to measure and record local solicited adverse events and body temperature. Subjects will also record solicited local and systemic adverse events (reactogenicity) in the diary in the evening after vaccination and then daily for the next 7 days at approximately the same time each day. Diaries should be completed at home by the subject (or parent, legal guardian or caregiver, as applicable). For illiterate subjects or those having difficulty completing the diary independently, the sites will make arrangements to have the diary completed according to their local practice. A modified diary is available for pre-verbal children. Subjects will be instructed to contact the investigator immediately in case they experience an unsolicited adverse event (not listed on the diary card) or for any severe (grade 3) solicited adverse event (listed on the diary card).

Subjects in Groups 2 and 3 from Cohort 1 will come for an additional visit on Day 15, and will have blood drawn for immunogenicity assessments.

In all groups, subjects will come to the site at 7 days after each vaccination as indicated in the [Time and Events Schedule](#). The subject's diary will be reviewed by study-site personnel. The investigator will examine the injection site for occurrences of erythema, induration/swelling, pain/tenderness or itching at these visits in order to complete the relevant parts of the CRF. Blood samples will be taken for safety (all subjects, after each vaccination) and immunogenicity (Cohorts 1 and 2a only, after boost vaccination) evaluations.

#### **9.1.4. Post-vaccination Phase**

In all groups, subjects will come to the site at 21 and 42 days after the boost vaccination as indicated in the [Time and Events Schedule](#). The investigator will examine the injection site for occurrences of erythema, induration/swelling, pain/tenderness or itching at these visits in order to complete the relevant parts of the CRF.

All adverse events, serious adverse events, IREs and pregnancies will be collected and documented on the CRF, together with the information on any concomitant medications. For reporting of IREs, refer to Section 12.3.3.

Subjects will also have blood drawn for immunogenicity assessments at the specified visits in the [Time and Events Schedule](#). Refer to Section [9.4](#) for further details on the immunogenicity evaluations.

Subjects will be instructed to contact the investigator before the next visit (ie, 6 months post-boost) if they experience any adverse event or intercurrent illness that they perceive as relevant and/or can be possibly related to study vaccine in their opinion.

### **9.1.5. Long-term Follow-up**

When all subjects in a cohort have completed their 6-month post-boost visit or discontinued earlier, that cohort will be unblinded to the sponsor. All subjects within a cohort will be followed in a blinded manner by the site until the last subject in that cohort has completed the study. Any subject who completed either the 6-month post-prime and/or the Day 365 visit prior to approval of Amendment 2 was required to attend the 6-month post-boost and the Day 365 visit after approval of Amendment 2.

Serious adverse event information and IREs will be collected until the end of the study, and concomitant therapies should only be recorded if given in conjunction with serious adverse events and IREs. Pregnancies will be reported until the end of the study. Subjects will have blood drawn for immunogenicity assessments at the 6-month post-boost and Day 365 visits. Refer to Section [9.4](#) for further details on the immunogenicity evaluations. Physical examinations will be performed as indicated in the [Time and Events Schedule](#).

Approximately 90 healthy adult subjects in Cohort 1 (Groups 1 and 2, at selected sites) will participate in a substudy. Refer to Section [9.1.7](#) for procedures to be followed for subjects participating in the Cohort 1 substudy.

### **9.1.6. Procedures in Case of a Study Pause**

A study pause can affect subjects that are either awaiting prime vaccination or boost vaccination. After approval is granted to restart the study, subjects who are awaiting prime vaccination and whose screening period is longer than the protocol-defined 8 weeks as a result of the study pause, will be allowed to rescreen once (following the screening procedures described in Section [9.1.2](#), excluding TOU). These subjects need to sign a new ICF/assent. Subjects that are rescreened due to the pause must have new safety laboratory assessments (including HIV, FSH [if applicable], ECG, hematology, biochemistry, urinalysis, vital signs and physical examination) within 28 days of the prime vaccination. The TOU does not need to be repeated. After screening, these subjects will follow the same study procedures as those subjects who were unaffected by the study pause (described in Sections [9.1.3](#) to [9.1.5](#)).

Subjects who are outside the protocol-defined boost vaccination window due to the study pause may choose to receive a late boost vaccination, if allowed by the sponsor and/or the relevant oversight authorities. Visit windows for the subjects who elect to receive a late boost vaccination are summarized in [Table 4](#). These subjects need to sign a specific ICF/assent. Subjects who agree

to the late boost vaccination will follow the same post-boost vaccination schedule as those subjects whose boost vaccination was unaffected by the study pause (see Section 9.1.4).

Note: For female subjects of childbearing potential, it should be confirmed that adequate birth control measures were used from at least 28 days before the prime vaccination **and boost vaccination**, with a negative serum  $\beta$ -hCG pregnancy test at screening and a negative urine test immediately prior to each study vaccination (see Section 4).

**Table 4: Visit Windows for Subjects Who Elect to Receive a Late Boost Vaccination**

Visit Description	Day	Window
Seven Days Post-prime Vaccination	Day 8 for all groups	$\pm 2$ days
Fourteen Days Post-prime Vaccination (only in Groups 2 and 3 from Cohort 1)	Day 15 for Group 2 and Group 3	$\pm 2$ days
Boost Vaccination		
Seven Days Post-boost Vaccination		$\pm 2$ days
Twenty-one Days Post-boost Vaccination		$\pm 3$ days
Forty-two Days Post-boost Vaccination		$\pm 3$ days
Follow-up 6 Months Post-boost		$\pm 15$ days
Follow-up 1 Year Post-prime	Day 365 for all groups	$\pm 30$ days

Visit windows for the subjects who are not willing or not allowed to receive a late boost vaccination are summarized in Table 5. These subjects need to sign a specific ICF/assent. All post-prime vaccination visits need to be performed despite the interruption in dosing. After the 7-day post-prime and 14-day post-prime (only in Groups 2 and 3 from Cohort 1) visits, these subjects will be followed every 3 months after the prime vaccination for safety only (and immunogenicity on the 6-month and 1-year post-prime visits), until Day 365 (see Additional Time and Events Schedule for subjects who do not receive a boost vaccination because of a study pause). Information for these time points (except for the 6-month and 1-year post-prime visits) may be collected either by telephone contact, visit to the site or by a home visit, according to local practice. For subjects in Groups 2 and 3 from Cohort 1, failure to obtain the blood samples for immunogenicity assessments on the additional visit on Day 15 will be considered as a minor protocol deviation.

**Table 5: Visit Windows for Subjects Who are Not Willing or Not Allowed to Receive the Late Boost Vaccination**

Visit Description a	Day	Window
Seven Days Post-prime Vaccination	Day 8 for all groups	±2 days
Fourteen Days Post-prime Vaccination (only in Groups 2 and 3 from Cohort 1)	Day 15 for Group 2 and Group 3	±2 days
Three Months Post-prime Vaccination b	Day 90 for all groups	±30 days
Six Months Post-prime Vaccination	Day 180 for all groups	±30 days
Nine Months Post-prime Vaccination b	Day 270 for all groups	±30 days
One Year Post-prime vaccination	Day 365 for all groups	±30 days

a Subjects will be asked to return to the site approximately every 3 months after the prime vaccination for safety assessments, until the 1-year post-prime follow-up visit (note: the 3-month and 9-month post-prime visits may be conducted by best local practice, see footnote b). In case the subject is unable to return for these visits, this will not constitute a major protocol deviation and subjects will be considered lost to follow-up.

b The 3-month and 9-month post-prime visits may be conducted by best local practice: either by telephone contact, site visit or home visit.

Adverse events, whether serious or non-serious, will be collected at all visits from signing of the ICF onwards until 42 days after the last vaccination (ie, Day 42 post-prime vaccination for subjects who did not receive a boost vaccination). Thereafter, reporting will be limited to all serious adverse events and IREs up to the subject's last study-related procedure. Solicited local and systemic adverse events (reactogenicity, see below) will be reported by the subject until 7 days after each administration of study vaccine. Adverse events will be followed by the investigator as specified in Section 12. Subjects will be instructed to contact the investigator before the next visit (ie, 6 months post-boost visit, or 3 months post-prime visit for subjects who are not willing or not allowed to receive a late boost vaccination) if they experience any adverse event or intercurrent illness that they perceive as relevant and/or can be possibly related to study vaccine in their opinion.

Subjects will have blood drawn for immunogenicity assessments as indicated in the [Time and Events Schedule](#) and [Additional Time and Events Schedule](#) (for subjects who do not receive a boost vaccination because of a study pause). Refer to Section 9.4 for further details on the immunogenicity evaluations. Physical examinations and vital signs will be performed as indicated in the [Time and Events Schedule](#) and [Additional Time and Events Schedule](#) (for subjects who do not receive a boost vaccination because of a study pause).

### 9.1.7. Cohort 1 Substudy (Third Vaccination)

The [Cohort 1 Substudy Time and Events Schedule](#) summarizes the frequency and timing of safety, tolerability and immunogenicity measurements and evaluations applicable to this substudy. Details for all study procedures are provided in the following paragraphs. Additional unscheduled study visits may be required if in the investigator's opinion, further clinical or laboratory evaluation is needed.

Subjects who received a late boost vaccination or did not receive the boost vaccination at all due to a study pause will not be included in the Cohort 1 substudy.

#### Visit Windows

If a subject did not receive study vaccine on the planned day of vaccination, the timings of the next visits post-vaccination (see [Cohort 1 Substudy Time and Events Schedule](#)) will be determined relative to the actual day of vaccination. Visit windows that will be allowed are summarized in [Table 6](#). The subject should be encouraged to come within these time windows.

**Table 6: Visit Windows**

Visit Description	Day a	Window
Third Vaccination (12-15m pp)	3 rd Vaccination	
Four Days Post Third Vaccination	Day 5 Post 3 rd Vaccination	±1 days
Seven Days Post Third Vaccination	Day 8 Post 3 rd Vaccination	±2 days
Twenty-one Days Post Third Vaccination	Day 22 Post 3 rd Vaccination	±3 days
Follow-up 6 Months Post Third Vaccination	Day 180 Post 3 rd Vaccination	±15 days
Follow-up 1 Year Post Third Vaccination	Day 365 Post 3 rd Vaccination	±30 days

a The day of administration of the third vaccination is Day 1 of the substudy. Similarly, D2 Post 3rd vaccination is the second day of the substudy, ie, 1 day after the third vaccination.

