**NOTE:** The day of administration of the third vaccination is Day 1 of the Cohort 1 substudy. Similarly, D2 Post 3rd vaccination is the second day of the Cohort 1 substudy, ie, 1 day after the third vaccination.

- a. All subjects will be followed up in a blinded manner by the site for the collection of serious adverse event information, immediate reportable events, and for blood draws for immunogenicity assessments until the last subject in that cohort has completed the study.
- b. Subjects eligible for the third vaccination are members of Cohort 1 (Groups 1 or 2) who consented to participate in the substudy. Approximately 90 subjects from Cohort 1 will be recruited at selected sites. For subjects who receive the third vaccination, the timings of the next post third vaccination visits will be determined relative to the actual day of the third vaccination.
- c. Informed consent form to enter in the Cohort 1 substudy must be provided and signed before the first substudy-related activity.
- d. After the third vaccination, subjects will remain at the site for a total of 30 ( $\pm 15$ ) minutes post-vaccination to monitor for the development of any acute reactions, or longer if deemed necessary by the investigator. Solicited and unsolicited adverse events emerging during the observation period at the site will be recorded in the case report form (CRF).
- e. Only for women of childbearing potential.
- f. Prior to study vaccine administration.
- g. An abbreviated, symptom-directed examination will be performed as indicated by the investigator.
- h. During the long-term follow-up, a physical examination should only be performed when related to serious adverse events and immediate reportable events.
- i. Includes blood pressure, pulse/heart rate (at rest) and body temperature.
- j. Subjects will use the subject diary to document solicited local and systemic adverse events (reactogenicity) in the evening after the third vaccination and then daily for the next 7 days at approximately the same time each day. Diaries should be completed at home by the subject. For illiterate subjects or those having difficulty completing the diary independently, the sites will make arrangements to have the diary completed according to their local practice.
- k. Non-serious adverse events will be reported until 28 days after the third vaccination. Pregnancies will be reported from signing of the informed consent form (ICF) until the end of the study.

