Day 85 (84 days Post-dose 1)	[82; 88]	[71; 98]	85
Day 141 (140 days Post-dose 1)	NA	[99; 168]	-
Day 197 (196 days Post-dose 1)	NA	[169; 224]	-
Day 253 (252 days Post-dose 1)	NA	[225; 280]	-
≥Day 281 (≥280 days Post-dose 1) ^d	NA	≥281	-
Day 365 (364 days Post-dose 1)	[335; 395]	≥281	365
After Second (Dose 2) Vaccination but Prior to Third (Dose 3) Vaccination			
Day 36 (7 days Post-dose 2)	[6; 10]	[2; 15]	8
Day 64 (7 days Post-dose 2)			
Day 92 (7 days Post-dose 2)			
Day 148 (7 days Post-dose 2)	NA	[16; 101]	22
Day 204 (7 days Post-dose 2)			
Day 260 (7 days Post-dose 2)			
≥Day 289 (7 days Post-dose 2)			
Day 50 (21 days Post-dose 2)	[19; 25]		

Time Interval (Label on Output)	Time Interval PP ^a (Day)	Time Interval IG ^b (Day)	Target Time Point (Day)
Day 78 (21 days Post-dose 2)	NA		
Day 106 (21 days Post-dose 2)			
Day 162 (21 days Post-dose 2)			
Day 218 (21 days Post-dose 2)			
Day 274 (21 days Post-dose 2)			
≥Day 303 (21 days Post-dose 2)			
Day 209 (180 days Post-dose 2)	[166; 196]	[102; 196]	181
Day 237 (180 days Post-dose 2)			
Day 265 (180 days Post-dose 2)			
Day 321 (180 days Post-dose 2)	NA		
Day 377 (180 days Post-dose 2)			
Day 433 (180 days Post-dose 2)			
≥Day 462 (180 days Post-dose 2)			
Day 365 (364 days Post-dose 1) ^c	[335; 395]	≥222	365
Day 365 (Pre-dose 3) ^f	[335; 395]	≥365	-
After Third (Dose 3) Vaccination			
Day 369 (4 days Post-dose 3)	[4; 6]	[2; 6]	5
Day 372 (7 days Post-dose 3)	[6; 10]	[7; 15]	8
Day 386 (21 days Post-dose 3)	[19; 25]	[16; 101]	22
Day 545 (180 days Post-dose 3)	[166; 196]	[102; 273]	181
Day 730 (365 days Post-dose 3)	[335; 395]	≥274	365

^a The analysis based on the per protocol (PP) analysis set will be restricted to data points that fall within this window (ie, protocol-defined window).

^b The analysis based on the immunogenicity (IG) analysis set will be restricted to data points that fall within this window.

^c This analysis visit (Day 15) applies only to subjects in Groups 2 and 3 of Cohort 1.

^d This analysis visit is only applicable to the sensitivity analysis of subjects in Group G (ie, ≥281-day interval vaccination schedule) as shown in [Table 3](#) below. For the other analyses (ie, non-sensitivity), this will correspond to the Day 365 analysis visit.

^e For the windows after Dose 2 administration, only Day 365 (364 days Post-dose 1) window is taken with respect to the day of Dose 1 administration.

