^f This analysis visit applies only to the subjects in the substudy (ie, Groups 1 and 2 subjects in Cohort 1 who received 3rd vaccination). For this visit, the assessment closest (but prior) to the vaccination should be used. If this visit coincides with the Day 365 (Day 365 Post-dose 1) visit, then the assessment should be assigned to both visits.

NA: Not applicable.

Note 1: The analysis windows and target days are based on the relative day (ie, with respect to the reference day [day of Dose 1, Dose 2 or Dose 3 administration]). The counting restarts from the day of a vaccination (ie, clock reset).

Note 2: Derivation of changes from pre-dose should be performed with respect to the reference value.

Time Interval (Label on Output)	Time Interval PP ^a (Day)	Time Interval IG ^b (Day)	Target Time Point (Day)
------------------------------------	--	--	----------------------------

Note 3: Immunogenicity sample collection at Day 141, Day 197, Day 253 and Day 281 visits were not planned according to the protocol. However, these visits were recorded for some Cohort 1 subjects due to the study pause (ie, late second [Dose 2] vaccination). If the analysis visit window contains the day of actual boost vaccination for these visits, then the assessment closest to the vaccination will be used.

Note 4: The same (ie, with respect to the number days since boost vaccination) post-boost visits are labeled differently. Day 36, Day 50 and Day 209 apply only to the 28-day interval schedule, Day 64, Day 78 and Day 237 apply to the 56-day interval schedule. Day 92, Day 106 and Day 265 apply only to the 84-day interval schedule. Day 148, Day 162 and Day 321 apply only to the 140-day interval schedule. Day 204, Day 218 and Day 377 apply only to the 196-day interval schedule. Day 260, Day 274 and Day 433 apply only to the 252-day interval schedule. \geq Day 289, \geq Day 303 and \geq Day 462 apply only to the \geq 281-day interval schedule.

Note 5: All assignments will be made in chronological order. Once an assessment is assigned to an analysis window, it will no longer be used for a later window.

Table 2: Analysis Periods

Phase	Period	Interval	
		From	To
Screening		00:00 on the date of signing the informed consent form	One minute prior to Dose 1 administration on Day 1

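### The SAP's per protocol window for the 6-month sample after the third vaccination (Days 166 to 196) is one day later than the protocol window it says it is (Days 165 to 195)

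*Protocol*

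**What the plan says.** Protocol Section 9.1.7, Table 6, lists the 6-month follow-up in the Cohort 1 substudy as "Day 180 Post 3 rd Vaccination" with a window of plus or minus 15 days. The footnote to the day column states the convention ("The day of administration of the third vaccination is Day 1 of the substudy"), and a note under the Cohort 1 Substudy Time and Events Schedule repeats it: "The day of administration of the third vaccination is Day 1 of the Cohort 1 substudy".

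SAP Section 2.1, Table 1, carries this visit in the row beginning "Day 545 (180 days Post-dose 3". The row has a per protocol window of [166; 196], an immunogenicity-set window of [102; 273] and a target day of 181. Footnote a gives the per protocol column its force: "The analysis based on the per protocol (PP) analysis set will be restricted to data points that fall within this window (ie, protocol-defined window". Note 1 under the table says that "The counting restarts from the day of a vaccination (ie, clock reset".

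SAP Section 3, which lists changes to the planned analysis, mentions only the redefinition of the two immunogenicity analysis sets. It declares no change to this window.

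**The concern.** Footnote a makes the protocol's visit window the rule for which data points enter the per protocol summaries, and Section 2.3 of the SAP makes that set the primary one for immunogenicity. For this row the SAP then states a different window from the protocol's. Sites schedule by Table 6, so a sample drawn on a permitted day can be left out while one drawn a day late is counted. What is at stake is the per protocol antibody summary six months after the third dose, and whether the SAP's description of its own window is true.

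**Working it through.** **Inputs**
- Protocol Table 6, days after the third vaccination: Day 5 ±1, Day 8 ±2, Day 22 ±3, Day 180 ±15, Day 365 ±30, with the dose day as Day 1.
- SAP Table 1, per protocol windows after Dose 3: [4; 6], [6; 10], [19; 25], [166; 196], [335; 395], with targets 5, 8, 22, 181 and 365.
- Protocol Table 3, 6 months post-boost: "Day 209 for Group 1", Day 237 for Group 2 and Day 265 for Group 3, each ±15, with the boost on Day 29, 57 or 85.

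**Step 1: the counting convention.** The SAP's baseline is Day 1, its count restarts at each dose, and 4, 7 and 21 days after Dose 3 have targets 5, 8 and 22. So the dose day is Day 1 in both documents.

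**Step 2: protocol window = day ± allowance, against the SAP.**

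| Visit after Dose 3 | Protocol | SAP per protocol | Agree? |
|---|---|---|---|
| 4 days | 5 ± 1 = 4 to 6 | 4 to 6 | yes |
| 7 days | 8 ± 2 = 6 to 10 | 6 to 10 | yes |
| 21 days | 22 ± 3 = 19 to 25 | 19 to 25 | yes |
| 6 months | 180 ± 15 = 165 to 195 | 166 to 196 | no |
| 1 year | 365 ± 30 = 335 to 395 | 335 to 395 | yes |

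**Step 3: the SAP's own figure.** [166; 196] is 181 ± 15. It is the right window after the boost: 209 − 29 + 1 = 181, 237 − 57 + 1 = 181, and 265 − 85 + 1 = 181.

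**Step 4: could the protocol's Day 180 mean 180 elapsed days?** That would give relative Day 181 and reproduce [166; 196]. But it contradicts the Table 6 footnote. Applied to the other rows, it would turn Day 5 ± 1 into 5 to 7 and Day 365 ± 30 into 336 to 396, where the SAP has [4; 6] and [335; 395]. The SAP's 1-year row is labelled as 365 days after Dose 3 yet has target 365, which is Table 6's day number. Counting 365 elapsed days would give 366.

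**Step 5: which days differ.** Days 166 to 195 are common to both windows: 195 − 166 + 1 = 30 of 31. Day 165 is in the protocol window only, and Day 196 is in the SAP window only. A Day 165 sample falls in no other per protocol window, since the neighbours are [19; 25] and [335; 395].

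**Step 6: size.** Approximately 90 subjects are planned, including placebo recipients. If the 5:1 allocation carries into the substudy (an assumption), 90 × 5/6 = 75 received active vaccine. With visits spread evenly over the 31 protocol days, the expected number on Day 165 is 75/31 = 2.4 to 90/31 = 2.9, and none fall on Day 196. With an even spread over the 32 days from 165 to 196, each edge day gets 75/32 = 2.3 to 90/32 = 2.8. With visits clustered near the target, both are close to 0.

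**The case against.** The strongest reply is that the SAP row is coherent in itself. Its label counts 180 elapsed days (365 + 180 = 545), which is relative Day 181 when the dose day is Day 1, and 181 ± 15 gives the stated window. The protocol itself counts six months in two ways: relative Day 181 after the boost and Day 180 after the third dose. Using one interval after both doses is a defensible analysis choice. This stands as far as it goes, and it means that changing only the target would leave the label out of step. It does not rescue footnote a, which says the window is the protocol's, or Section 3, which declares no departure. The SAP's 1-year row also follows Table 6's day number over its own label.

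A reader might infer more than the documents support:

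- **That the post-boost row was copied to Dose 3.** The values are identical, which suggests a carry-over, but nothing in the documents says so.
- **That the target day distorts sample selection.** The closest-to-target rule acts only when a subject has two or more assessments in one window, and the substudy schedules a single 6-month draw. With two samples on days a < b, and ties going to the later one, target 180 picks b when a + b ≤ 360 and target 181 picks b when a + b ≤ 362. The choice differs only if the days sum to 361 or 362.
- **That subjects leave the per protocol set.** Footnote a restricts data points. Set membership under SAP Section 2.3 does not depend on this window.
- **That 90/31 is an upper bound.** It is an expected count under even spread. It includes placebo recipients and takes no account of the further per protocol restrictions in Section 2.3.

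**Conclusion.** The mismatch is real. As written, the SAP's per protocol rule misclassifies samples taken on relative Days 165 and 196 after the third dose, under a label that says it follows the protocol. This is the only one of the five post-dose 3 windows that departs from Table 6.

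It is a minor point. The visit supplies serum for an exploratory humoral time point (Protocol Section 11.1.3) in a study with no formal hypothesis testing. SAP Section 2.3 repeats the analysis on the immunogenicity set, whose window [102; 273] contains both edge days. Safety and the secondary endpoint, ELISA at 21 days post-boost, are untouched. The estimate of 2 to 3 samples at an edge day rests on the even-spread assumption and on 75 to 90 contributing subjects. The documents give no actual visit dates, so the true number could be zero. They offer no basis for saying that the 6-month persistence result would be materially changed.

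**What to change.** In SAP Table 1, change the per protocol window of the 6-month post-dose 3 row to [165; 195] and its target day to 180, and leave the immunogenicity-set window at [102; 273]. This is the direct remedy, because footnote a defers to the protocol. Check the row label at the same time: with target 180 the visit is 179 elapsed days after the dose, so a label of 180 days needs rewording or a footnote, and the matching entry in the time-point list of SAP Section 6.2.1.3 should be checked.

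If relative Day 181 is intended, so that the 6-month summaries after Dose 2 and Dose 3 refer to the same interval, keep the row, record it in SAP Section 3 as a departure from Protocol Table 6, and correct footnote a for this row.

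The first option costs an edit to one table row, a label check and the matching programming change. The second needs text only. Neither needs new data. The choice should be made without reference to the unblinded results.
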